15. APPENDICES

APPENDIX A – PEDIATRIC RISK OF MORTALITY (PRISM II) SCORE ^[27]

ORGAN SYSTEM	MEASURE
Respiration	PaO ₂ to FiO ₂ Ratio, P _a CO ₂ , Resp. Rate
Coagulation	Protime, PTT
Liver	Serum Total Bilirubin
Cardiovascular	Systolic BP, Diastolic BP, Heart rate
Central nervous system	Glasgow Coma Score, Pupillary Reflexes
Metabolic	Serum potassium, calcium, glucose, bicarbonate glucose

ORGAN SYSTEM	MEASURE	FINDING	POINTS
Respiration	PaO ₂ to FiO ₂ Ratio (please see Pulmonary System Conversion Table for Non-ventilated Pts)	200 – 300 mmHg	2
		<200 mmHg	3
	P _a CO ₂	51-65 mmHg	1
		>65	5
	Respiratory Rate (breath/min)	51-70	1
		>70 or Apnea	5
Coagulation	Protime or Partial Thromboplastin Time	1.5 x control	2
Liver	Serum Total Bilirubin	>3.5 mg/dL	6
Cardiovascular	Systolic Blood Pressure (mmHg)	150-200 or 65-75	2
		>200 or 50-64	6
	Diastolic Blood Pressure (mmHg)	>110	6
	Heart Rate (beat/min)	>150 or <80	4
Central Nervous System	Glasgow Coma Score	<8	6
	Pupillary Reactions	Unequal or dilated	4
		Fixed and dilated	10
Metabolic	Potassium (mEq/L)	3.0 – 3.5 or 6.5 – 7.5	1
		<3.0 or >7.5	5
	Calcium (mg/dL)	7.0 – 8.0	2
		12.0 – 15.0 or <7.0	6
	Glucose (mg/dL)	40-60 or 250 – 400	8
		<40 or >400	8
	Bicarbonate (mEq/L)	<16 or >32	3

Conventions used for the above table include:

- PaO₂ is in mmHg and FiO₂ in percent from 0.21 to 1.00.

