5.3 EXCLUSION CRITERIA

1. Threshold blood pressure of 80/40 mmHg-- patients with both a systolic blood pressure of less than 80 mmHg and a diastolic blood pressure of less than 40 mmHg.
2. Irreversible brain damage based on available historical and clinical information.
3. Patients with a solid organ transplant or those with a bone marrow or stem cell transplant in the previous 100 days or who have not engrafted.
4. Acute or chronic use of circulatory support device, other than ECMO, such as LVADs, RVADs, BIVADs.
5. Presence of preexisting advanced chronic renal failure (i.e., ESRD) requiring chronic renal replacement therapy prior to this episode of acute kidney injury or with pre-existing chronic kidney disease (CKD) defined as a eGFR <30 ml/min/1.73m 2 . Patients who have never seen a pediatric nephrologist will be assumed not to have pre-existing CKD.
6. AKI occurring in the setting of burns, obstructive uropathy, vasculitis, scleroderma renal crisis, atheroembolism, functional or surgical nephrectomy, cyclosporine or tacrolimus nephrotoxicity.
7. Received >12 hour of CRRT (not including SCUF on ECMO) during this hospital admission or prior to transfer from an outside hospital.
8. Received >1 hemodialysis treatment during this hospital admission or prior to transfer from an outside hospital.
9. Metastatic malignancy which is actively being treated or may be treated by chemotherapy or radiation during the subsequent three month period after study therapy.
10. Chronic immunosuppression with the exception of corticosteroids up to a dose of 10 mg per day.
11. HIV or AIDS.
12. Severe chronic liver failure as determined by standard diagnostic requirements.

13. Current Do not Attempt Resuscitation (DNAR), Allow Natural Death (AND), or withdrawal of care status, or anticipated change in status within the next 7 days.
14. Patient not expected to survive 28 days because of an irreversible medical condition. (This is not restrictive to AKI, and may include situations such as the presence of irreversible brain damage, untreatable malignancy, inoperable life threatening condition, or any condition to which therapy is regarded as futile by the PI.)
15. Any medical condition that the Investigator thinks may interfere with the study objectives.
16. Physician refusal.
17. Dry weight <15 kg.
18. Platelet count <15,000/mm³.

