Besides the test of the hypothesis the study is focused on observable, empirical and laboratory determinations of patient safety while on the SCD. Previous human trials have been conducted on the SCD device and the protocol contains a review of AE and SAE data from all SCD human studies and findings from those studies contributed to constructing the investigative safety profile. Safety endpoint measures specified in the protocol include adverse events, laboratory safety parameters, vital signs, ventilation status and hemodynamic variables. Device integrity and performance measurements are also defined as are circumstances which demand premature termination of SCD treatment.

Prolonged exposure to the SCD is anticipated to result in superior outcomes, although as noted above, this pilot study is not designed to assess for efficacy. However, we understand that a minimum amount of exposure to the SCD will be required for an appropriate safety analysis and for making any inference regarding efficacy. The ppCRRT experience demonstrated that the majority of patients (201/370) received CRRT for 1 to 7 days and exhibited 65% survival (Symons et al CJASN 2007 Table7). Assuming our trial includes patients with similar illness severity, we have established a 72 minimum number of hours a patient will be treated with the SCD to be included in the final outcome analysis.

This trial is an early safety efficacy study but is not powered for statistical significance. Insights into a comparison of historical controls matched to SCD treated patients will utilize the ppCRRT Registry to match for: etiology of AKI, co-morbidities, CRRT modality, dose and form of anticoagulant, adverse events. [10].

The ppCRRT Registry has data fields for the primary reason for CRRT, including AKI and its cause, as well as co-morbidities which will be matched for primary organ system involvement. The CRRT modality was evenly distributed between convective and diffusive modality, with 60% of the convective modalities provided as CVVH and 40% as CVVHDF. The anticoagulant protocol will be standardized with ACD-A/CaCl₂ and all centers used the same protocol in ppCRRT Registry as outlined in this study protocol. Thus, the ppCRRT Registry dataset will be able to be matched to our study patient cohort. Also as noted above, patients will be matched for age, size and PRISM II score.

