The Prospective Pediatric CRRT (ppCRRT) database will be used as a control for the CRRT treatment related factors including: patient age, gender, primary cause of AKI, total treatment duration, CRRT modality (CVVH, CVVHD, CVVHDF), CRRT small solute clearance (ml/1.73m²/hour), baseline estimated GFR (using the original Schwartz formula, which was used in the ppCRRT), urine output in the 24 hours prior to CRRT initiation (ml/kg/hour), percent fluid overload at CRRT initiation based on admission ICU weight, vasoactive medication number at time of CRRT initiation and mean airway pressure at CRRT initiation.

An additional analysis will also evaluate patients who have achieved targeted iCa levels during 90% of treatment time and those who do not.

In summary this protocol meets all criteria necessary for clinical scientific inquiry related to a test of hypothesis in a well monitored environment focused on patient safety during the conduct of the study. Basic statistics will be performed on the data sets along with historical data comparisons and subjected to subset analysis where appropriate. The results will help to guide the design of a future pivotal study of this device.

The rational for therapy, study objectives and endpoints, design, inclusion and exclusion criteria are explicitly defined. Patient safety parameters are well documented including safety reporting, safety observations and assays, procedures for patient withdrawal and study discontinuation criteria along with monitoring device integrity and performance. Lastly, a review of all prior SCD human study safety data is included in the protocol for full disclosure to study investigators and the informed consent document includes a full description of all known and potential risks of the device treatment.

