APPENDIX A (Continued)
PEDIATRIC RISK OF MORTALITY (PRISM II) SCORE ^[27]

GLASGOW COMA SCORE

The Glasgow Coma Score (GCS) is scored between 3 and 15, 3 being the worst and 15 the best. It is composed of the three parameters listed below:

Best Eye Response (4)

1. No eye opening
2. Eye opening to pain
3. Eye opening to verbal command
4. Eyes open spontaneously

Best Verbal Response (5)

1. No verbal response
2. Incomprehensible sounds
3. Inappropriate words
4. Confused
5. Oriented

Best Motor Response (6)

1. No motor response
2. Extension to pain
3. Flexion to pain
4. Withdrawal from pain
5. Localizing pain
6. Obeys commands

A Coma Score of 13 or higher correlates with a mild brain injury, 9 to 12 is a moderate injury and 8 or less a severe brain injury.

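### The PRISM II table in Appendix A has missing extreme bands, an unexplained glucose tie and a conflicting FiO2 unit, so a stated matching variable can be mis-scored

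*Combined protocol and SAP*

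**What the plan says.** Appendix A prints the PRISM II points table and cites an outside source for it. The combined protocol and SAP contains no other rule for scoring PRISM II. Four entries matter here:

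- **Calcium (mg/dL):** 7.0 to 8.0 scores 2, and "12.0 – 15.0 or <7.0" scores 6. Nothing is listed above 15.0.
- **Systolic pressure (mmHg):** 150 to 200 or 65 to 75 scores 2, and above 200 or 50 to 64 scores 6. Nothing is listed below 50.
- **Glucose (mg/dL):** "40-60 or 250 – 400" scores 8. Below 40 or above 400 also scores 8.
- **FiO2:** the convention under the table gives it "in percent from 0.21 to 1.00". The Pulmonary System Conversion Table in the same appendix lists it as a percentage, from 24 to 99+.

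The score is taken at baseline (Section 6.3 and Appendix F). Section 11 says that "patients will be matched for age, size and PRISM II score", with the ppCRRT registry supplying the controls. A longer list in Section 11, for which the registry database "will be used as a control for the CRRT treatment related factors including: patient age, gender, primary cause of AKI" and several further items, does not include PRISM II. Section 11 also says the trial "is not powered for statistical significance".

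**The concern.** A severity score should not fall as the patient gets worse, and one patient should not be able to earn two scores from one appendix. Read literally, Appendix A allows both. Splitting glucose into two bands with equal points also serves no purpose, which suggests a copying slip.

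This matters because the outcome comparison has no concurrent control arm. Mortality and dialysis dependency are set against historical patients, and Section 10 plans an efficacy evaluation against them after 16 patients. Such a comparison depends on each matching variable being measured the same way on both sides. In a group of 16, one patient mis-scored by 6 points moves the cohort mean by 6 / 16 = 0.4 points.

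**Working it through.** The plan gives no figure to reproduce, so the check is an inspection of the table followed by simple arithmetic.

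**1. Do points rise from the milder to the more extreme band?** Eight measures in Appendix A have two bands.

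| Measure | Milder band | More extreme band |
|---|---|---|
| PaO2/FiO2 ratio | 2 | 3 |
| PaCO2 | 1 | 5 |
| Respiratory rate | 1 | 5 |
| Systolic pressure | 2 | 6 |
| Pupils | 4 | 10 |
| Potassium | 1 | 5 |
| Calcium | 2 | 6 |
| Glucose | 8 | 8 |

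Seven rise and only glucose is tied.

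**2. Do the scales cover their extremes?** Applying the rows literally:

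- Systolic pressure 64 scores 6, 50 scores 6, 49 scores 0 and 45 scores 0.
- Calcium 12.5 scores 6, 15.0 scores 6 and 15.5 scores 0.

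Each gap costs a patient 6 − 0 = 6 points. Adding the highest points for every measure gives 3 + 5 + 5 + 2 + 6 + 6 + 6 + 4 + 6 + 10 + 5 + 6 + 8 + 3 = 75, so 6 points is 6 / 75 = 8% of the printed maximum.

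**3. How large could the glucose error be?** The intended points are not in the documents. Assume that 8 is right for the extreme band and that the milder band should score some whole number m from 1 to 8. The over-score is then 8 − m, from 0 (the tie is intended) to 7, and 7 / 75 = 9.3% of the maximum. If instead the extreme band was meant to score above 8, the error is an under-score in that band, and the documents do not bound it.

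**4. What does the FiO2 unit do?** Use values from the conversion table.

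- Saturation 99% converts to PaO2 145, and 1 L/min by nasal cannula to FiO2 24%. As a fraction, 145 / 0.24 = 604, which scores 0. As a percentage, 145 / 24 = 6.0, which falls below 200 and scores 3.
- Saturation 97% converts to PaO2 96, and 5 L/min by cannula to FiO2 40%. As a fraction, 96 / 0.40 = 240, which scores 2. As a percentage, 96 / 40 = 2.4, which scores 3.

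The first pair uses the highest PaO2 and lowest FiO2 in the conversion table, so with percentages no converted patient can exceed a ratio of 6.0 and all score 3. The discrepancy is 0, 1 or 3 points per patient.

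**5. How many patients could the systolic gap reach?** Section 5.3 excludes "patients with both a systolic blood pressure of less than 80 mmHg and a diastolic blood pressure of less than 40 mmHg". A patient with systolic pressure below 50 who is still eligible needs a diastolic pressure of at least 40, which is a pulse pressure below 10 mmHg. The other route is a low reading elsewhere in the 12-hour baseline window of Section 6.3.

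**6. Can a site total be rescored?** Section 6.3 lists blood pressure, heart rate, the laboratory values and blood gases. It does not itemise respiratory rate, coma score or pupils, so a total alone could not be rebuilt from the listed data.

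**The case against.** The strongest reply is that these are blemishes a competent scorer would see past. Nobody would give 0 points to a systolic pressure of 45, and ratio bands of 200 and 300 only make sense with FiO2 as a fraction. Two glucose bands with equal points work as one wide band, and the table uses single bands for heart rate, bicarbonate and bilirubin. A misread glucose cell cannot be excluded. PRISM II matching is stated once and is missing from the longer factor list, which carries other markers of severity such as vasoactive medication number, mean airway pressure and fluid overload. The trial makes no claim to power.

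Much of this stands. The glucose tie is an anomaly, not a proven error, and few patients are likely to reach the systolic gap. The documents give no reason to think calcium above 15.0 is common. It does not clear the table: the two open extremes and the unit conflict lie in the wording, and relying on each scorer to repair a rule silently is what a printed table should prevent.

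A reader might go further and infer that trial patients are over-scored, matched to sicker controls, and the device flattered. The documents do not support that. The calcium and systolic gaps under-score patients, which pushes the other way, and the glucose error has no known sign or size. Nor can a cohort-wide shift be estimated, because the share of patients in the milder glucose band is not given. A reader might also take the coma-score row as another error, since it scores below 8 while the accompanying text calls "8 or less a severe brain injury". That text describes brain injury and is not a scoring rule.

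**Conclusion.** The point holds as a defect in a scoring rule that the trial relies on for a stated matching variable. Per patient, the error is up to 6 points on calcium or systolic pressure, 0 to 7 in the milder glucose band (assumed range, with the extreme band's 8 taken as right), and 0 to 3 if FiO2 is entered as a percentage.

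The effect on the comparison cannot be sized. The documents give no caliper or weight for PRISM II and do not say which table or time window produced the registry scores. If both sides used this table in the same way, the faults mainly coarsen the match. If the registry used another, the shift is systematic, with a net direction that is unknown. No sample size, alpha or power figure changes. The correction should be made before matching.

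**What to change.** Before any matching:

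1. Check Appendix A against its cited source and against the scoring used in the registry.
2. Correct or confirm the glucose row, complete the calcium and systolic rows, and state one FiO2 unit for both the points table and the conversion table.
3. Record the component values on the CRF, including coma score, pupils and respiratory rate, and score trial patients centrally with the same table and time window as the registry scores. The documents do not show that registry component values exist, so the trial scoring should be aligned to however the registry totals were produced.
4. Rescore anyone already scored from the printed table.
5. Say in Section 11 whether PRISM II is a matching variable, since its lists disagree.

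The cost is an appendix correction, a few extra CRF fields and some analysis work. Patients already enrolled may need a return to source records for the missing components.

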APPENDIX A (Continued)
PEDIATRIC RISK OF MORTALITY (PRISM II) SCORE ^[27]

GLASGOW COMA SCORE

The Glasgow Coma Score (GCS) is scored between 3 and 15, 3 being the worst and 15 the best. It is composed of the three parameters listed below:

Best Eye Response (4)

1. No eye opening
2. Eye opening to pain
3. Eye opening to verbal command
4. Eyes open spontaneously

Best Verbal Response (5)

1. No verbal response
2. Incomprehensible sounds
3. Inappropriate words
4. Confused
5. Oriented

Best Motor Response (6)

1. No motor response
2. Extension to pain
3. Flexion to pain
4. Withdrawal from pain
5. Localizing pain
6. Obeys commands

A Coma Score of 13 or higher correlates with a mild brain injury, 9 to 12 is a moderate injury and 8 or less a severe brain injury.

APPENDIX A (Continued)
PEDIATRIC RISK OF MORTALITY (PRISM II) SCORE ^[27]

PULMONARY SYSTEM CONVERSION TABLE

O₂ Saturation Conversion Table	Conversion Table for FiO₂
Pulse oximetry O ₂ saturation may be used for calculating PaO ₂ /FiO ₂ ratio when ABG not available	When measured on mask or nasal cannula

SaO ₂ (%)	Calculated PaO ₂
80	44
81	45
82	46
83	47
84	49
85	50
86	52
87	53
88	55
89	57
90	60
91	62
92	65
93	69
94	73
95	79
96	86
97	96
98	112
99	145

Nasal Cannula	
100% O ₂ Flow Rate (L/min)	FiO ₂ (%)
1	24
2	28
3	32
4	36
5	40
6	44
Oxygen Mask	
100% O ₂ Flow Rate (L/min)	FiO ₂ (%)
5-6	40
6-7	50
7-8	60
9	90
10	99+
Mask with Reservoir Bag	
100% O ₂ Flow Rate (L/min)	FiO ₂ (%)
6	60
7	70
8	80

APPENDIX B – DEFINITIONS OF ACUTE KIDNEY INJURY

Acute Kidney Injury

Acute Kidney Injury (AKI) is sudden loss of the ability of the kidneys to excrete wastes, concentrate urine, and conserve electrolytes. AKI is due to a variety of etiologies. These conditions are found in circumstances of acute injury and conform to one of the following criteria:

- Increase in SCr by ≥ 0.3 mg/dl (≥ 26.5 μ mol/L) within 48 hours or:
- Increase in SCr to ≥ 1.5 times baseline, which is known or presumed to have occurred within the prior 7 days or:
- Urine volume <0.5 ml/kg/h for 6 hours

(Note: pre-renal, vascular, , and obstructive etiologies are excluded on clinical or other diagnostic grounds.)

AKI develops predominantly due to the injury and necrosis of HPTC (Human Proximal Tubular Cells). AKI is caused by ischemia of the kidneys or by exposure to nephrotoxic agents. Risks for AKI include injury or trauma with resulting damage to the muscles, recent major surgery, blood transfusion reaction, septic shock or other forms of shock, and severe hypotension longer than 30 minutes.

Any condition that causes a reduction in the amount of blood being pumped by the heart may cause AKI. Liver disease and damage caused by diabetes mellitus (diabetic nephropathy) may predispose a person to the condition. AKI can also be caused by exposure to nephrotoxic agents (e.g., aminoglycoside antibiotics), antifungal agents (e.g., amphotericin), medications to prevent rejection of transplanted organs (e.g., cyclosporine), dye used for radiographic studies, and other toxins. In SCD studies, patients with AKI due to a variety of etiologies are eligible for study participation. As noted above, pre-renal, vascular, and obstructive etiologies are excluded on clinical or other diagnostic grounds.

APPENDIX C – DEFINITIONS OF ORGAN FAILURE AND SEPSIS [28]**A. SEPSIS**

Sepsis is defined in this protocol as the presence (probable or documented) of infection together with two or more of the following systemic manifestations of infection:

Age	2-5 years	6-12 years	13-18 years	19-22 years
Tachypnea ¹ (breaths / min)	>22	>18	>14	>14
Tachycardia (beats / min)	>140	>130	>110	>90
Hyper/Hypothermia (all ages)	>38.5°C or <36°C			
WBC ($\times 10^3$ /mm3)	>15.5 or <6	>13.5 or <4.5	>11 or <4.5	>12 or <4.0

¹. Patient meets this criteria if mechanically ventilated, not related to underlying neuromuscular disease or the receipt of general anesthesia.

B. NON-RENAL ORGAN FAILURE

At least one non-renal organ failure (defined as receiving mechanical ventilation [12] or at least one vasoactive medication to treat hypotension) OR presence (proven or suspected) of sepsis.

APPENDIX D – ENDPOINT DEFINITIONS

ALL-CAUSE MORTALITY:

All cause mortality is defined as in-hospital, 28-day and 60-day all cause mortality.

DIALYSIS DEPENDANCY AT DAY 60:

Dialysis dependency at day 60 is defined as patient not receiving any form of intermittent or continuous renal replacement therapy at or within 3 days of 60 days post enrollment in the study with no plans for additional intermittent or continuous renal replacement therapy.

PATIENT SAFETY:

Adverse events, laboratory safety parameters, vital signs, EKG, ventilation status and hemodynamic variables.

DURATION OF RENAL SUPPORT:

The duration of renal support will be defined as the numbers of days from the initiation of renal replacement therapy (start of observation period) to final dialysis treatment. Duration of renal support will be censored if the patient is still dialysis dependent at the time of death or are dependent at day 60.

RECOVERY OF RENAL FUNCTION:

Recovery of renal function will be defined as lack of need for continuous dialysis support on day 28, and will be classified as yes or no at day 28. Subjects who were alive at day 28 will be included in the analysis. Patients who remain dialysis dependent at study completion (day 60) or time of death will be categorized as having no recovery of renal function.

ASSESSMENT OF SCD █ INTEGRITY AND PERFORMANCE:

The SCD █ will be evaluated for the presence of clotting, leaking or any other malfunction.

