	
17. Dry weight of <15 kg.18. Platelet count <15,000/mm³ at time of screening.19. Concurrent enrollment in another interventional clinical trial. Patients enrolled in clinical trials where only measurements and/or samples are taken (NO TEST DEVICE OR TEST DRUG USED) are allowed to participate.20. Use of any other Investigational drug or device within the previous 30 days.
Evaluation Plan	The primary evaluation of this study will be safety and all-cause mortality or dialysis dependency through 60 days post-enrollment. Additional endpoints will be time on CRRT, total ICU and hospital days. Mortality and dialysis dependency rates will be compared to historical controls.

LIST OF ABBREVIATIONS

[figure not shown]
AE	Adverse Event
AKI	Acute Kidney Injury
ARDS	Acute Respiratory Distress Syndrome
ARF	Acute Renal Failure
ATN	Acute Tubular Necrosis
BW	Body Weight
iCa	Ionized Calcium
CBC	Complete Blood Count
CRF	Case Report Form
CRRT	Continuous Renal Replacement Therapy
CTICU	Cardiothoracic Intensive Care Unit
CVVH	Continuous Veno-Venous Hemofiltration
CVVHD	Continuous Veno-Venous Hemodialysis
CVVHDF	Continuous Veno-Venous Hemodiafiltration
ECS	Extra Capillary Space
ICU	Intensive Care Unit
MICU	Medical Intensive Care Unit
nriCa	Non Recommended Ionized Calcium Range
ppCRRT	Prospective Pediatric CRRT Registry
PRISM	Pediatric Risk of Mortality
RAD	Renal Assist Device
riCa	Recommended Ionized Calcium Range
SAE	Serious Adverse Event
SCD	Selective Cytopheretic Device
SICU	Surgical Intensive Care Unit
SIRS	Systemic Inflammatory Response Syndrome
SOFA	Sequential Organ Failure Assessment
WBC	White Blood Cell
UADE	Unanticipated Adverse Device Effect

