3.2 STUDY ENDPOINT

In this Pilot study four (4) domains of interest have been designated. The four (4) domains are:

1. Patient Safety: Safety Endpoint Measures include adverse events, laboratory safety parameters, vital signs, EKG, ventilation status and hemodynamic variables.
2. Clinical Efficacy: The Primary Clinical Efficacy Endpoint Measure is in-hospital; 28 and 60-day all-cause mortality. Time to renal recovery and necessity for chronic dialysis up to day 60 will also be

determined. Additional efficacy endpoints include time to intensive care unit (ICU) discharge, and time to hospital discharge.

3. Device Integrity and Performance: The Endpoint Measure is SCD use without failure. This measure will help assess the integrity and performance of the SCD device.
4. SCD Mode of Action: Exploratory Endpoint Measures will include inflammatory cytokines, cell activation parameters and biomarkers at clinical sites with this capability.

Endpoints are defined in **Appendix D**.

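### Appendix D defines day-60 dialysis dependency as being off dialysis: the sentence is inverted and must be corrected before analysis

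*Combined protocol and SAP*

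**What the plan says.** Section 3.2 makes Appendix D the source of endpoint definitions: "Endpoints are defined in Appendix D". Under its day-60 heading the appendix states: "Dialysis dependency at day 60 is defined as patient not receiving any form of intermittent or continuous renal replacement therapy". The sentence goes on to set a 3-day window around day 60 and to require that no more RRT is planned.

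Two neighbouring entries use the term in its ordinary sense. Duration of renal support is "censored if the patient is still dialysis dependent at the time of death or are dependent at day 60". The recovery entry reads: "Patients who remain dialysis dependent at study completion (day 60) or time of death will be categorized as having no recovery of renal function". Section 3.2 describes the quantity of interest as "necessity for chronic dialysis up to day 60".

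Dependency at days 28 and 60 appears in the Synopsis secondary objective and in the Section 3.1 primary objective. The Synopsis Evaluation Plan states: "The primary evaluation of this study will be safety and all-cause mortality or dialysis dependency through 60 days post-enrollment", and later "Mortality and dialysis dependency rates will be compared to historical controls". Section 10 gives the DSMB mortality and dialysis dependency to assess under effectiveness.

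**The concern.** The governing sentence has its sign reversed. Followed as printed, a survivor freed from dialysis counts as dependent and a survivor still on dialysis does not. No other formal definition of dependency in the document overrides it.

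The comparison with historical controls is the most exposed use. If trial patients were scored by the printed sentence and registry patients in the ordinary sense, the two rates would measure opposite things. If the sponsor instead departs from the sentence at analysis, it will be choosing an endpoint definition after open-label outcomes are known. The choice would be the obvious one, but it should be on paper beforehand.

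**Working it through.** **1. The entries side by side.** The duration entry counts days up to the final dialysis treatment and censors patients who are dependent at day 60. Censoring makes sense only for a patient whose final treatment has not yet been seen, that is, one still on dialysis. The recovery entry classes patients who are dependent at day 60 as not recovered, which again fits only patients on dialysis. Both entries need the opposite of the printed day-60 definition.

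**2. The sponsor's earlier scoring.** Section 2.4.1 (ARF-002) equates renal recovery with dialysis independence. For the SCD-003 subgroup kept in the recommended calcium range (Section 2.5.3), the inputs are:

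- Table 6: deaths 3/19 (SCD) and 11/27 (CRRT alone), so 16 survivors in each arm.
- Table 8: dependent survivors 0/16 and 4/16.
- Table 9: death or dependency 3/19 and 15/27.

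With dependent meaning on dialysis, 3 + 0 = 3 of 19 (15.8%) and 11 + 4 = 15 of 27 (55.6%), which is Table 9 exactly. Pearson chi-square without continuity correction gives p = 0.0325 for Table 8 (printed 0.033) and p = 0.0065 for Table 9 (printed 0.007). With the Appendix D sentence, the counts would have been 3 + 16 = 19 of 19 and 11 + 12 = 23 of 27, which do not match. The sponsor has therefore used the ordinary meaning before.

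**3. Size if coded literally (illustration only).** Let m be mortality and d the share of survivors on dialysis at day 60. Take death or dependency as the composite.

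- Intended: m + (1 - m)d
- Literal: m + (1 - m)(1 - d)
- Difference: (1 - m)(1 - 2d), which is positive whenever d is below 50%

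The inputs are assumptions taken from the protocol's figures:

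- m = 35% comes from the 65% survival in Section 11. That figure is for the 201 of 370 registry patients on CRRT for 1 to 7 days, and no 60-day horizon is stated.
- m = 50% comes from the Synopsis rationale.
- d = 10-20% is the rationale's figure for AKI patients who do not recover renal function. It is not stated for survivors.

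| m | d | Intended | Literal | Difference (points) |
|---|---|---|---|---|
| 0.35 | 0.10 | 0.35 + 0.065 = 41.5% | 0.35 + 0.585 = 93.5% | 52 |
| 0.35 | 0.20 | 0.35 + 0.13 = 48% | 0.35 + 0.52 = 87% | 39 |
| 0.50 | 0.10 | 0.50 + 0.05 = 55% | 0.50 + 0.45 = 95% | 40 |
| 0.50 | 0.20 | 0.50 + 0.10 = 60% | 0.50 + 0.40 = 90% | 30 |

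**4. Is information lost?** No RRT-status data are lost. Sections 6.5.2 and 6.5.3 collect presence and dates of RRT, so status can be derived under either definition. Plans for further RRT, which the definition also uses, are not listed at those contacts. The contact may fall anywhere from day 60 to day 67, while the definition's window is 3 days around day 60.

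**5. Day 28.** There is no day-28 dependency entry. The nearest reads: "Recovery of renal function will be defined as lack of need for continuous dialysis support on day 28". It names continuous dialysis only, covers patients alive at day 28, and also brings in day-60 status. Section 7.3 item 1 foresees a switch from CRRT to intermittent hemodialysis. A survivor on intermittent dialysis at day 28 who is off it by day 60 could therefore be scored as recovered at day 28. The documents give no modality data at day 28, so this cannot be sized.

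**The case against.** The best defence is that nobody would be misled. The rest of Appendix D, Section 3.2 and the earlier trials all point to the ordinary meaning. Sites record RRT presence and dates, not a derived flag, so the error can be put right at analysis. The trial has no power calculation, so no sample size, power or alpha depends on the sentence. All of this stands. It limits the harm, but it does not make the printed rule correct, and Section 3.2 sends the reader to that rule.

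Three stronger readings are tempting, and the documents do not support them.

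- A reader might infer that the reported results will be wrong by 30 to 52 points. That gap needs literal coding, which the surrounding text argues against. It also needs a composite that only the Evaluation Plan suggests: the plan itself goes on to speak of mortality and dependency rates, and Section 3.2 names mortality as the primary clinical efficacy measure.
- A reader might infer that patients off dialysis would be censored and classed as not recovered. Those entries speak of patients who are still, or who remain, dependent, and their own wording resists that reading.
- A reader might take the SCD-003 counts under literal coding (19/19 against 23/27) as a forecast of a reversed treatment effect. They come from an adult post hoc subgroup of a randomized trial and predict nothing about this single-arm pediatric pilot.

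**Conclusion.** The day-60 sentence is wrong as written: it defines independence under the name dependency. It is a drafting error with a recoverable intent and no loss of RRT-status data. Because it is the only formal definition of an endpoint used in the objectives, the evaluation plan, the historical comparison and the DSMB review, it must be corrected before any analysis. The mortality endpoint is untouched.

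The figures of 87-95% literal against 41.5-60% intended show what following the sentence would do. They hold only under literal coding, the composite reading of the Evaluation Plan, and the assumed m and d. The direction of the error needs only that fewer than half of survivors are still on dialysis.

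The missing day-28 definition is a secondary clarification and does not carry the same weight.

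**What to change.** In Appendix D:

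1. Define day-60 dependency as being on any RRT, intermittent or continuous, inside the existing 3-day window around day 60, or having further RRT planned. Keep the present wording under the name dialysis independence.
2. Use that single window and apply it to the recorded RRT dates relative to day 60, not to the date of the contact (day 60 to 67).
3. State that the dependency rate is among patients alive at day 60, and that deaths count as events in any composite. As printed, a patient who has died is also not receiving RRT.
4. Record whether further RRT is planned at the contact, if the case report form does not already do so.
5. As a secondary edit, give day-28 dependency the parallel wording, and state that day-28 recovery means free of both continuous and intermittent RRT.

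The cost is a change of wording and possibly one yes/no item. Reported day-28 recovery may be slightly less favourable if some survivors are on intermittent dialysis at that time.
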